#### 8.1.2 SECONDARY OUT COME MEASURES

Not applicable

#### 8.1.3 EXPLORATORY MEASURES

- Pain scale score assessment
- Grip strength
- Wrist range of motion assessed by Investigator
- PRWE score assessment
- Modified Mayo Wrist Score assessment

## 8.2 SAFETY MEASURES

The incidence and severity of AEs related to the study will be captured. Investigators will inquire about the occurrence of any AEs at all study visits and unscheduled visits. Subjects will also be asked to self-report AEs throughout the duration of the study. Adverse events will be recorded.

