### 9.3.4 SAFETY ANALYSIS

Safety analyses will include the incidence and severity of adverse events observed over the study assessment period. These will be tabulated and presented overall and by relatedness, severity, and preferred term.

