## 11 ADVERSE EVENTS

Throughout the course of the study, AEs will be monitored and reported on an AE CRF, including seriousness, severity, relationship to device, and action taken. If AEs occur, the first concern will be the safety of the study participants. The Investigator and the research staff will monitor each subject closely, and record any complications that may arise, though not anticipated. Study clinician will use his/her medical judgment to do whatever is necessary to help treat the problem. Potential risks and/or side effects include:

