### 11.1 DEFINITIONS

#### 11.1.1 ADVERSE EVENT

An adverse event (AE) is any untoward medical occurrence in a subject that does not necessarily have a causal relationship with the treatment. An adverse event can therefore be any unfavorable and unintended sign (including an abnormal laboratory finding), symptom, or temporal disease, whether or not related to the study assessment(s)/questionnaire(s).

Pre-existing disease or symptoms thereof prior to study enrollment are not considered AEs unless the condition recurs after the subject has recovered from the pre-existing condition, or the condition worsens in intensity or frequency during the study. Normal post-operative sequelae will not be recorded as adverse events. Specifically, normal post-operative pain, swelling, tenderness, loss of skin sensation and ecchymosis within the first two weeks postoperative, requiring normal levels of medication will not be recorded; all abnormal intensity or duration will be recorded and considered an adverse event as well as following the two-week post-operative period.

Adverse events will be monitored throughout the study. At each post-baseline visit, the Investigator will begin querying for adverse events by asking each subject a general, nondirected question such as "Have you had any changes to your condition since your last visit?" Previous adverse events and changes in therapy/concomitant medications should be updated. Directed questioning and examination will then be done as appropriate. All reported adverse events will be documented.

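### Section 9.3.4 does not tabulate adverse events by treatment arm, so the planned safety outputs would not compare PRP with saline; one sentence in 8.2 also conflicts with the rest of the plan on which events are captured.

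*Combined protocol and SAP*

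**What the plan says.** **Table layout.** After stating that incidence and severity of AEs will be analysed, section 9.3.4 gives the layout: "These will be tabulated and presented overall and by relatedness, severity, and preferred term". Treatment arm is not named there, in 8.2, or anywhere in section 11. By contrast, section 9.5 names the treatment and placebo groups for the efficacy t-tests.

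**Scope of capture.** Section 8.2 opens with "The incidence and severity of AEs related to the study will be captured". Its next sentence is "Investigators will inquire about the occurrence of any AEs at all study visits and unscheduled visits". Section 11 says "AEs will be monitored and reported on an AE CRF, including seriousness, severity, relationship to device, and action taken". Section 11.1.1 defines the term without a causal requirement, "An adverse event (AE) is any untoward medical occurrence in a subject that does not necessarily have a causal relationship with the treatment", and adds "All reported adverse events will be documented".

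**Early events.** Section 11.1.1 also says "Normal post-operative sequelae will not be recorded as adverse events". It names pain, swelling, tenderness, loss of skin sensation and ecchymosis in the first two weeks, where medication needs are normal. The exemption is bounded: "all abnormal intensity or duration will be recorded and considered an adverse event as well as following the two-week post-operative period".

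**Who is analysed.** Section 9.1 removes discontinued subjects from data analysis, states no exception for safety, and defines no safety population.

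**The concern.** Both arms undergo debridement and a wrist injection. In one patient it is hard to tell whether a local reaction came from the surgery or from PRP; the randomised comparison between arms is what separates them. Tabulating by relatedness is no substitute, because relatedness is a case-by-case opinion. If the safety tables are produced exactly as 9.3.4 lists them, that comparison is never shown.

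The wording of 8.2 adds a smaller risk. A site that followed its first sentence literally would collect too few events, and the relatedness split in 9.3.4 would then lack its unrelated category.

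**Working it through.** **1. The plan's own figure.** The documents give no safety rate or safety sample size. The one figure available is 24 per arm (9.6: difference 15 points, SD 18, two-sided 5%, power 80%). The normal approximation gives n = 2 × [18 × (1.960 + 0.842) / 15]² = 22.6, rounded up to 23. The two-sample t-test version gives 23.6, rounded up to 24, with power 80.7% at 24 per arm. The stated 24 reproduces.

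**2. What a pooled table shows.** The rates are assumed, since the documents give none: 20% on PRP and 5% on saline.

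- Expected events: 24 × 0.20 = 4.8 and 24 × 0.05 = 1.2.
- Pooled: (4.8 + 1.2) / 48 = 12.5%, or 6 of 48.
- Splits of 3 and 3, 5 and 1, or 6 and 0 (25% against 0%) all give 6 of 48. The pooled row cannot tell them apart.

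**3. What by-arm tables could support.** Power at 24 per arm, two-sided 5%, with rates p₁, p₂ and mean p̄: Φ{[|p₂ − p₁|√n − 1.96√(2p̄(1 − p̄))] / √(p₁(1 − p₁) + p₂(1 − p₂))}. For 5% against 20%: (0.15 × 4.899 − 1.96 × 0.4677) / 0.4555 = −0.40, so power is about 35%. Fisher's exact test was also evaluated over all outcomes.

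| Assumed saline, PRP | Normal approx. | Fisher | n per arm for 80% (normal approx.) |
|---|---|---|---|
| 5%, 20% | 35% | 24% | 76 |
| 10%, 30% | 41% | 31% | 62 |
| 20%, 40% | 32% | 24% | 82 |
| 10%, 40% | 68% | 60% | 32 |

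An observed 5 of 24 against 1 of 24 has a two-sided Fisher p of about 0.19. With no events in 24, the one-sided 95% upper bound is 1 − 0.05^(1/24) = 11.7%. By-arm tables would therefore be descriptive.

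**4. Scope, side by side.** The first sentence of 8.2 restricts capture to study-related events. Against it stand the next sentence of 8.2 (ask about any AE), section 11 (relationship is a field on the form, so it is not an entry filter), and 11.1.1 (no causal requirement; every reported event documented). One sentence is out of line with the rest.

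**5. Early events, side by side.** Section 11 lists seven foreseeable risks. Two of them, pain and swelling, are also among the sequelae exempt for two weeks under 11.1.1. The first scheduled post-operative visit is month 1 (6.1.3), so scheduled pain scores do not cover that window. Abnormal intensity or duration is recorded, but the plan does not define normal.

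**6. Denominator.** Section 7.1 lists death, alternative treatment and missed visits among the reasons for discontinuation. Read with 9.1, the AEs of such subjects could drop out of the safety tables.

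**The case against.** The strongest case against is that little is lost. Section 9.3.4 does not forbid a split by arm, allocation is known for each subject, and recorded events can be split at analysis without new data. This stands in part. A reader might infer that the trial cannot show whether PRP adds harm; the documents do not support that. They support only that the planned outputs would not show the comparison.

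A reader might also infer from 8.2 that only related events are collected. Taken with the rest of 8.2, section 11 and 11.1.1, that reading fails.

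A third tempting reading is that an unblinded investigator filters the events. The plan blinds subjects and medical staff outside the operating room. It does not state the investigator's status or who classifies AEs, and section 10.2 allows delegation. Unblinded classification is possible but not established.

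It is also fair to say that the two-week exemption is narrower than it first looks. Excess early reactions have a stated route into the record through the abnormal-intensity clause, self-report and unscheduled visits. What remains is an undefined boundary and the overlap with the foreseeable risks.

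Finally, the illustrative rates are invented, and even by-arm tables would have low power. Both are true. They limit what the tables can prove, but they are no reason to pool the arms.

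**Conclusion.** The point holds as a reporting gap and a wording conflict. The safety layout omits treatment arm in a trial whose purpose is PRP against saline, and the first sentence of 8.2 disagrees with the sections that govern AE recording. Both should be corrected.

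No stated figure changes and the sample size stays at 48. The size of the gap depends on event rates that the documents do not give. Under the assumed rates, a 15-point difference does not appear in a pooled 12.5%. Across the four assumed pairs, power at 24 per arm runs from 24% to 60% (Fisher) or 32% to 68% (normal approximation), so the gain is a visible descriptive comparison and not a formal safety test.

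The early-events issue is secondary. Normal pain and swelling in the first two weeks that go unrecorded cannot be recovered by splitting tables later, but events judged abnormal are recorded.

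**What to change.** - **9.3.4:** present the number and percentage of subjects with AEs and with serious AEs by treatment arm received, then by relatedness, severity and preferred term within arm. State that these are descriptive, with no formal testing.
- **9.1:** define the safety set as all injected subjects, including those who discontinue, so that the exclusion of discontinued subjects does not reach the safety tables.
- **8.2:** change the first sentence to cover all AEs, whether or not related, in line with 11 and 11.1.1.
- **11 and 11.1.1:** reconcile the two-week exemption with the listing of pain and swelling as foreseeable risks, and state that the resulting rule is applied identically in both arms. Asking about early reactions at month 1 is one option, but it relies partly on recall and adds low-grade entries; the point does not depend on it.

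The cost is a few sentences in one protocol amendment, which needs IRB approval, and arm columns in the AE tables. The changes to 8.2, 9.1 and 9.3.4 need no extra visits or subjects and no data beyond what 11.1.1 already requires.

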## 8.3 SUMMARY OF METHODS OF DATA COLLECTION

Paper documents will be used to collect standardized assessments for PRWE scores, Modified Mayo Wrist scores, and pain assessment. Study-specific information, such as Investigator reviews and assessments will be recorded directly in the subject's medical record.

Grip strength and wrist range of motion will be recorded by the Investigator in the subjects' medical record.

## 9 STATISTICAL PROCEDURES

Every attempt will be made to collect complete data and limit the occurrence of missing data. Due to the descriptive nature of all analyses, no imputation of missing data will be performed. Descriptive summaries will be based on all observations available within each of the relevant analysis populations.

Descriptive statistics will be presented for key outcome measures.

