## 9.5 EXPLORATORY ANALYSES

The difference in preoperative versus postoperative outcomes within groups (treatment versus placebo) will be tested for significance using paired t-tests. The significance of differences in preoperative versus postoperative outcomes between groups (treatment and placebo group) will be analyzed using 2-sample t-tests. Additional analyses of possible relationships between outcomes may also be performed using appropriate inferential tests.

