## 9.6 SAMPLE SIZE CALCULATION

The trial will be powered to detect a difference in post-treatment PRWE scores between groups of 15, deemed to be clinically significant by the investigators. The standard deviations for PRWE scores previously published after treatment for TFCC tears ranges from 6.6 to 20.5. To detect a mean difference in post-treatment PRWE score of 15 points ( $SD = 18$ ) with a two-sided significance level of 5% and power of 80% with equal allocation to two arms would require 24 patients in each arm of the trial.

Subjects will be assessed per standard of care of their clinical requirement and qualification for surgery and upon subject's decision to participate in the study. The difference in preoperative and postoperative outcomes will be analyzed to

determine which group has the most improvement based on the following outcomes: pain scale scores, wrist range of motion, PRWE scores, and Modified Mayo Wrist scores.

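### Section 9 rules out imputation because all analyses are descriptive, yet 9.5 and 9.6 plan powered significance tests, and no named test uses the partial follow-up of a subject who misses the tested visit

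*Combined protocol and SAP*

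**What the plan says.** Section 9 sets the missing-data rule and its reason: "Due to the descriptive nature of all analyses, no imputation of missing data will be performed". It adds: "Descriptive summaries will be based on all observations available within each of the relevant analysis populations".

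Section 9.5 then plans inference. Within-arm differences "will be tested for significance using paired t-tests". Differences "between groups (treatment and placebo group) will be analyzed using 2-sample t-tests". It also allows that "Additional analyses of possible relationships between outcomes may also be performed using appropriate inferential tests". No post-operative visit is named for any of these tests.

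Section 9.6 states: "The trial will be powered to detect a difference in post-treatment PRWE scores between groups of 15", and sizes the trial "with a two-sided significance level of 5% and power of 80% with equal allocation to two arms would require 24 patients in each arm". Section 5.1 randomizes exactly that number, 24 and 24.

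Three other sections decide who is left to analyse. Section 7.1 lists not completing scheduled visits among the reasons a subject may be discontinued. Section 9.1 excludes discontinued subjects from data analysis and makes the per-protocol set the primary group. Section 9.8 counts visit-window departures as deviations, and classes those that affect the primary endpoint as major.

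**The concern.** The rule on missing data rests on a premise that the plan contradicts. Once arms are compared by a significance test, missing values affect an estimate, a standard error and a p-value, and the plan should say how.

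A t-test on change needs both the pre-operative value and the tested post-operative value. A subject seen at months 1, 3 and 6 but not at year 1 contributes nothing to a year 1 comparison, although the month 6 score says a good deal about the missing one. Non-return over a year after wrist surgery may well be related to how the wrist is doing. If that relation differs between PRP and saline, the subjects who attend are no longer comparable across arms. Even if it does not, subjects are lost from a trial of 48 that has no allowance for loss.

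**Working it through.** **1. The plan's own figure.** Inputs from 9.6: difference 15, SD 18, two-sided 5%, power 80%, equal arms. Normal approximation: n = 2(1.96 + 0.84)² × 18² / 15² = 22.6, so 23 per arm. The exact two-sample t-test gives 78.9% power at 23 and 80.7% at 24. The stated 24 reproduces, provided that every randomized subject is evaluable.

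**2. Loss of precision.** The documents give no loss rate, so the rates here are assumed. The standard error is 18 × √(2/n). With 24 per arm it is 5.20. With 24 × 0.8 = 19.2 per arm it is 5.81, a ratio of √(24/19.2) = 1.12. Exact power for 15 points is 78.6% at 5% loss, 76.2% at 10%, 71.0% at 20% and 64.9% at 30%.

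**3. Bias.** Assumptions: SD 18 at each visit, 20% missing year 1, log-odds of missing year 1 changing by 1 per SD of the month 6 score, year 1 taken as the tested visit.

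- In an arm with this dependence, the attenders' mean month 6 score is shifted by about 3.1 points. This follows from a simulated shift of 1.55 points in the year 1 score at a month 6 to year 1 correlation of 0.5 (1.55/0.5 = 3.1).
- The shift in mean change is 3.1 × (correlation of month 6 with year 1 minus correlation of month 6 with baseline).
- Correlations 0.7 and 0.3: 3.1 × 0.4 = 1.2 points. Correlations 0.8 and 0.5: 3.1 × 0.3 = 0.9 points.
- Dependence in one arm only: bias about 0.9 to 1.2. Opposite dependence in the two arms: twice that, 1.9 to 2.5. Same dependence in both arms: the shifts cancel and the bias is zero.

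Trial-level simulation of the change t-test at these settings gave 1.0 to 1.4 points (one arm) and 2.0 to 2.4 (opposite). Over somewhat varied settings the range is about 1 to 3, or 7% to 20% of the 15-point target. A baseline-adjusted likelihood estimate using all visits had a bias of about 0.2 or less. Baseline adjustment at year 1 alone left 1.8 to 3.9 points, so it is the earlier visits that remove the bias.

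**4. Where the power gain comes from.** With baseline correlation r, the SD of change is 18 × √(2(1 − r)): 21.3 at r = 0.3 and 18.0 at r = 0.5. The residual SD after baseline adjustment is 18 × √(1 − r²): 17.2 and 15.6. Power for 15 points, with loss alike in both arms:

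| Analysis | r = 0.3 | r = 0.5 |
|---|---|---|
| Change t-test, nobody missing | 67% | 81% |
| Change t-test, 20% missing | 57% | 71% |
| Baseline-adjusted, attenders only, 20% missing | 75% | 83% |
| Baseline-adjusted repeated measures, 20% missing (simulated) | 76–77% | 83–86% |

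Baseline adjustment accounts for 18 and 12 percentage points. Using earlier visits adds about 1 to 3 more.

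**The case against.** The strongest reply is that the plan is less bare than it may look. A reader might infer that Section 9 forbids any handling of missing data, that every visit is tested on attenders, and that a non-returner's earlier visits are thrown away. The text does not support this. It bars imputation only; a likelihood model is not imputation, so it is unplanned rather than barred. Section 9.5 names no visit. Under the available-case rule earlier visits still count in their own summaries. Section 7.1 also asks for contact with non-returners and a recorded reason for discontinuation.

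It can also be said that the tests sit under exploratory analyses, that 9.3.1 makes the primary analysis descriptive, and that a four-visit model per outcome is heavy for 48 subjects. The placement is as stated, but these are the only between-arm comparisons named, and 9.6 sizes the trial for one.

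On size, much of the reply stands. Bias needs a dependence that differs by arm, in a trial where subjects and staff outside the operating room are blinded. In the patterns simulated it ran against PRP, and the rejection rate under no effect stayed between 4% and 7%; the reverse patterns of loss would reverse the sign. The model's near-zero bias follows from generating missingness from the recorded month 6 score.

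Finally, a model alone may not reach the subjects concerned. Sections 7.1, 9.1 and 9.8 can remove a non-returner entirely, earlier visits included. That is correct, and the fix has to cover it.

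**Conclusion.** The point holds, as a low-cost improvement that should be made. The reason given for ruling out imputation is contradicted by 9.5 and 9.6, and nothing specified for the tests uses partial follow-up or examines its effect.

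Precision is lost whatever the cause of missingness: at an assumed 20% loss, a 12% larger standard error, and 71% instead of 81% power on the plan's own SD. Bias is conditional: about 1 to 3 PRWE points if year 1 loss of about 20% is driven by the month 6 score differently in the two arms, and none if loss is alike in both.

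A reader might conclude that missing data explain most of the low power of the planned test, or that the late comparison is biased in any event. Neither follows. At a baseline correlation of 0.3 the change t-test has only 67% power with nobody missing, and when loss is not differential nearly all of the proposed model's gain is baseline adjustment. All sizes rest on assumed loss rates, correlations and mechanisms.

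**What to change.** - **Section 9:** delete the opening clause that gives the descriptive character of the analyses as the reason. The no-imputation rule can stay.
- **Section 9.5:** replace the between-group 2-sample t-tests with one mixed model for repeated measures per outcome. Response: months 1, 3, 6 and 12. Fixed effects: arm, visit, arm-by-visit and pre-operative value. Use an unstructured covariance with a simpler fallback named in advance, and Kenward-Roger degrees of freedom. Report the arm difference with its 95% CI at each visit.
- **Section 9.1:** apply the model to all randomized subjects with any post-operative value. State that a missed visit, a discontinuation under 7.1 or a visit-related deviation under 9.8 does not remove data already recorded.
- **Reporting:** tabulate missing visits by arm with reasons. For year 1 PRWE, add a sensitivity analysis that shifts the unobserved values by arm until the conclusion changes (tipping point).

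The cost is SAP wording and a little programming, with no new subjects, visits or data. It should be done before unblinding. The downsides are that the model assumes missingness depends on recorded values and does not correct loss driven by the unseen score, which is why the shift analysis is needed; and that with 48 subjects the covariance may have to be simplified.

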### 9.1 POPULATIONS FOR ANALYSES

All subjects will be included in the full analysis population. The per protocol population is defined as subjects who have not had any major protocol deviations throughout the study (Section 9.8) and will be analyzed as the primary study group. Other subgroups may be analyzed as detailed in the subgroup analyses section. Subjects that have been discontinued will be excluded from data analysis.

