#### 4.5 VISITS & PROCEDURES

Enrolled subjects will undergo baseline questionnaires/assessments and baseline imaging during their pre-operative visit. Once arthroscopic debridement is complete, patients will be randomized intraoperatively to treatment with PRP versus placebo (normal saline). Subjects and medical staff outside of the operating room will be blinded to treatment group throughout the study. Questionnaires/assessments will then be administered and performed at month 1, month 3, month 6 and year 1 post-operative visits. Follow-up imaging will be performed at 6 month post-operative visit.

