### 5 STUDY POPULATION CHARACTERISTICS

#### 5.1 NUMBER OF SUBJECTS

Forty-eight (48) subjects undergoing arthroscopic debridement for TFCC tears will be randomized intraoperatively to treatment with PRP (24 subjects) versus treatment with normal saline (24 subjects).

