## 7 STUDY INTERVENTION DISCONTINUATION AND PARTICIPANT DISCONTINUATION/WITHDRAWAL

### 7.1 EARLY DISCONTINUATION OF SUBJECTS

Each subject reserves the right to withdraw from the study at any time without jeopardy to her future medical care. All follow-up assessments and procedures

should be performed at the final study visit. For any subject who discontinues from the study, the date and reason for discontinuation will be recorded.

If a subject fails to return for one or more scheduled study visits, the Investigator will attempt to contact the subject to determine and document the reason the subject has failed to return and to encourage compliance with the study visit schedule.

A subject may be discontinued from the study for the following reasons:

- Subject did not undergo arthroscopic debridement as it was deemed not warranted by the Investigator
- Since enrollment in the study, subject has had alternative treatment that would otherwise affect the study questionnaire/outcomes data
- Subject does not complete scheduled follow-up visits per protocol
- Subject has died

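### Section 9.1 makes per-protocol the primary population and drops every discontinued subject, so the PRP-versus-saline comparison loses the protection of randomisation, and 24 per arm leaves no allowance for such exclusions

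*Combined protocol and SAP*

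**What the plan says.** Section 9.1 of the combined protocol and SAP contains three statements that bear on this point. It first says "All subjects will be included in the full analysis population". It then defines the per-protocol population as subjects free of major deviations, which "will be analyzed as the primary study group". It closes with "Subjects that have been discontinued will be excluded from data analysis". No other section gives the full analysis population a role.

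Section 7.1 governs discontinuation: "A subject may be discontinued from the study for the following reasons". Four reasons follow: debridement judged not warranted, "subject has had alternative treatment that would otherwise affect the study questionnaire/outcomes data", failure to complete the scheduled follow-up visits, and death. For subjects who leave early, it says that follow-up assessments "should be performed at the final study visit".

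On timing, Section 4.5 says "Once arthroscopic debridement is complete, patients will be randomized intraoperatively", and Section 6.3 agrees. Section 5.1 sets the allocation at "treatment with PRP (24 subjects) versus treatment with normal saline (24 subjects". Section 9.6 arrives at the same 24 per arm as the number needed.

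Section 9.8 calls a deviation major when it bears on how the primary endpoint is measured or interpreted. It does not say who decides, when, or whether that person is blind to arm. Section 9 rules out imputation.

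**The concern.** Randomisation makes the two arms comparable at the moment of allocation. Anything that later decides who is counted can undo that if it is related to arm or outcome. Alternative treatment is the clearest case. A subject whose wrist does badly may seek other treatment, may then be discontinued, and would disappear from the analysis. If that happens more often in one arm, the remaining subjects in that arm look better than the arm as randomised. The bias could favour either arm.

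The judgement points are open as well. Discontinuation is permitted rather than required, and the major or minor label in 9.8 is assigned by an unnamed person with no stated blinding.

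At stake is the comparison the trial was built for: Section 9.3 states a comparative hypothesis, 9.6 powers a between-group difference in PRWE, and 9.5 tests between-group differences with 2-sample t-tests. Each exclusion also comes out of a sample size that carries no allowance for loss.

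**Working it through.** **1. Which exclusions come after randomisation.** Sections 4.5 and 6.3 place randomisation after completed debridement. Set against the four reasons in 7.1:

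- Debridement not warranted: before randomisation, so exclusion does no harm to the comparison.
- Alternative treatment affecting outcomes: can arise after randomisation.
- Scheduled follow-up visits not completed: after randomisation.
- Death: can arise after randomisation.

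Major deviations under 9.8 can also arise after randomisation.

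**2. Internal consistency of 9.1.** If discontinued subjects are left out of data analysis without qualification, no analysed population can contain all subjects. The first and last sentences of the paragraph cannot both be applied.

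**3. The plan's own sample size.** Inputs from 9.6: difference δ = 15 PRWE points, SD σ = 18, two-sided α = 0.05, power 80%, equal allocation. The test is the 2-sample t-test of 9.5.

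Normal approximation: n = 2 × [σ(1.960 + 0.842)/δ]² = 2 × [18 × 2.802/15]² = 22.6, so 23 per arm.

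t-test: power = P(|T| > critical t), where T is noncentral t with n₁ + n₂ − 2 degrees of freedom and noncentrality λ = δ / [σ√(1/n₁ + 1/n₂)]. Solving for 80% gives n = 23.6, so 24 per arm. This reproduces the stated figure exactly and shows that it contains no allowance for loss.

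**4. Power as subjects are excluded** (δ = 15, σ = 18):

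| Analysed per arm | λ | Critical t | Power |
|---|---|---|---|
| 24 / 24 | 2.887 | 2.013 | 80.7% |
| 24 / 23 | 2.856 | 2.014 | 79.8% |
| 23 / 23 | 2.826 | 2.015 | 78.9% |
| 22 / 22 | 2.764 | 2.018 | 77.0% |
| 21 / 21 | 2.700 | 2.021 | 75.0% |
| 20 / 20 | 2.635 | 2.024 | 72.8% |

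The documents give no exclusion rate. Assuming 10% in each arm, 24 × 0.90 = 21.6 per arm on average and power is 76.2%. Assuming 20%, 24 × 0.80 = 19.2 and power is 71.0%.

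**5. Detectable difference at 80% power** (same σ and test): 14.9 points at 24 per arm, 15.6 at 22, 16.4 at 20.

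**6. Bias.** The documents give no discontinuation rate by arm and no outcomes of discontinued subjects, so neither its size nor its direction can be calculated.

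**The case against.** The strongest reply is that the plan presents itself as exploratory. The synopsis says that 48 subjects suffice for descriptive summaries and exploratory analyses, Section 9 calls all analyses descriptive, 9.3.1 summarises the primary outcome with descriptive statistics only, and the t-tests sit under the heading for exploratory analyses. This softens the power point. It does not touch the bias point: arm means computed after selective removal are distorted whether or not a test follows, and the plan still states a comparative hypothesis and a powered difference.

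A second reply is that the power loss is small beside the uncertainty in the SD. Section 9.6 cites published SDs from 6.6 to 20.5. At an SD of 16, 20 per arm still gives 82.4%; at 20.5, 24 per arm gives only 69.9% with nobody excluded. The normal approximation would leave about one patient per arm in hand. The calculation also concerns post-treatment PRWE, whereas 4.3 and 9.5 compare changes from baseline, whose SD is not given. All of this stands, so the power figures hold only on the plan's own inputs.

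Third, 7.1 has the investigator contact subjects who miss visits and encourage them to keep to the schedule, so a missed visit need not end in discontinuation. Subjects and medical staff not in the operating room are blinded, which limits removal driven by knowledge of the arm. Both points reduce the likely number of exclusions or their dependence on arm. Neither prevents removal that depends on outcome, and the blinding does not extend to those who were in the operating room.

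**Conclusion.** The concern holds and should be fixed before the analysis. Applied as written, Section 9.1 contradicts itself and bases the main comparison on subjects selected by events after randomisation. That conclusion rests on the text alone and needs no assumed rate.

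The bias could go either way, and its size is unknown. The power consequence is conditional on a 15-point difference, an SD of 18 and the t-test: one exclusion in total moves power from 80.7% to 79.8%, and losing four per arm moves it to 72.8%. Part of that loss would occur under any population definition if subjects leave without giving data, so it should not all be charged to the exclusion rule.

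**What to change.** - **Section 9.1:** define the primary population as all randomised subjects, analysed in their assigned arm with all observed data, including the final-visit assessments. Delete the sentence excluding discontinued subjects. State that subjects who consent but are never randomised, because debridement was not warranted, lie outside this population. Keep per-protocol as a sensitivity analysis.
- **Section 9.8:** name who classifies deviations, and require this to be done blind to arm and before unblinding.
- **Section 7.1:** separate having another treatment or missing a visit from ending data collection. Subjects in the first situation keep their scheduled outcome assessments unless they withdraw consent.
- **Section 9.6:** state that 80% power needs 24 evaluable subjects per arm, and give the power at 20 to 22 per arm (72.8% to 77.0%).

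The t-tests in 9.5 can stay; a mixed model over the visits is an option, not a requirement. Enrolling more subjects would restore power (for an assumed 10% loss, 24/0.90 = 26.7, so 27 per arm) but would not remove the bias, so it does not replace the change of population.

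The cost is wording in four sections, plus follow-up of a few more subjects at visits already scheduled. That follow-up is a real addition, because for subjects who leave, 7.1 provides assessments only at the final visit. There are two downsides: the estimate will include the effect of any alternative treatment, and the stated power will look slightly less favourable. Subjects who give no post-operative data will still be missing, since Section 9 excludes imputation; their number should be reported by arm.
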